8. ENDPOINT EVALUATION

8.1. Overview of Efficacy Analysis Methods

8.1.1. Multicenter Studies

ICH E3: 11.4.2.4; ICH E9: 3.2

8.1.2. Assessment Time Windows

SCIT/placebo injections were scheduled as close as possible to the target date as outlined in the Schedule of Events (Section 15.1). Any data collected outside of a visit window will still be included in any analyses of the scheduled visit.

National Institute of Allergy and Infectious Diseases
{Statistical Analysis Plan - Protocol #}

At the onset of the COVID-19 pandemic, all in-person study visits were suspended including all SCIT/placebo injections. All participant follow-up was conducted via telephone during this time. As in-clinic injection visits resumed, the following procedures were restricted: Spirometry, Nasal Lavage, Peak Flow, Nasal Allergen Challenge. Resumption of all study procedures was conducted via study-specific approvals reviewed by site and network leadership. Each participant whose therapy was interrupted was re-escalated to maintenance therapy. The first dose a participant received upon resumption of immunotherapy was based on their dose at the time of suspension of therapy, the time elapsed, and their reaction history (see Appendix B of the ICAC-28 protocol).

8.1.3. Missing Data

The primary method of handling missing efficacy data will be the use of complete case analysis for the primary analyses. Indeed, participants with missing data for the 12 months NAC will not be included in the ANCOVA with factors for arm and site and the respective baseline TNSS as a covariate.

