6.7 Premature Discontinuation of Investigational Agent

Participants who are unable to reach the minimum maintenance dose by 40 weeks following the start of dose escalation will be unable to proceed to the maintenance period and will have their study therapy discontinued (see Section 11.2.1 Discontinuation of Study Therapy; see Appendix B Study Restrictions Due to COVID-19).

Study therapy may be prematurely discontinued for any participant for any of the reasons identified in Section 11.2.1 Discontinuation of Study Therapy. Study therapy may also be prematurely discontinued for any participant if the study clinician believes that the study treatment is no longer in the best interest of the participant. Participants whose therapy is prematurely discontinued will be followed when possible for the duration of the study and seen for all remaining visits except Injection Visits.

7 Other Medications

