11.4 Follow-up after Study Therapy Discontinuation

Participants who discontinue study therapy after receiving one dose of investigational product will be asked to continue study follow-up for the remainder of the treatment period, using an altered visit schedule.

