5. ANALYSIS SAMPLES

[ICH E3: 11.4.2.6](#); [ICH E9: 5.2](#)

The following groups of participants will define samples for endpoint analysis:

- **Modified Intent-to-treat (ITT) sample:** All participants who are randomized, received at least one dose of study treatment, and receive at least one dose during the 12-month NAC. Participants will be analyzed according to the treatment arm to which they were randomized, regardless of the medication they actually received.
- **Safety sample:** All participants who sign consent and undergo study procedures at Screening. Participants will be analyzed according to the medication they actually received, regardless of the treatment arm to which they were randomized. Non-treatment-emergent adverse events (e.g., any adverse event that occurs before the first injection) will be summarized in all participants who are enrolled, while treatment-emergent adverse events (e.g., any adverse event that occurs on or after the first injection) will be summarized in the safety sample.
- **Per-protocol (PP) sample:** All participants who are randomized, are escalated to at least 0.4 mL of the 1:10 maintenance dose, and receive at least 3 doses of maintenance SCIT/placebo.

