8.2. Primary Endpoint

[ICH E9: 2.2.2-2.2.7](#)

Variable (Endpoint): Change in mean TNSS after 12 months of treatment with cockroach SCIT.

Population: Of all subjects defined by the study inclusion / exclusion criteria, the analysis population will include subjects who are in the modified ITT and per protocol populations.

Intercurrent events: All intercurrent events will be handled following hypothetical strategy (imputation). Missing data of this nature, as well as missing data due to withdrawal, will be multiple imputed as described above in section 7.1.3.

[figure not shown]
Population-level summary: Difference between treatment groups, Cockroach SCIT vs Placebo, in the change in mean TNSS after 12 months of treatment between the placebo and treatment arm.

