14. APPENDIX

14.1. Table of Estimands

Objective Clinical Category	Statistical Category	Estimand/Variable

Primary Objective: To compare efficacy of cockroach subcutaneous immunotherapy (SCIT) superiority within placebo/active in participants with participants with asthma and german cockroach sensitization with respect to:
		
Efficacy Category 1	Primary/MCP	
• Variable: Change in mean TNSS after 12 months of treatment with cockroach SCIT.• Population: Of all subjects defined by the study inclusion / exclusion criteria, the analysis population will include subjects who are modified ITT and per protocol population.• Intercurrent Event Strategy (IES): All intercurrent events will be handled following hypothetical strategy (imputation). Missing data of this nature, as well as missing data due to withdrawal, will be multiple imputed as described above in section 7.1.3.• Population Level Summary (PLS): Difference between treatment groups, Cockroach SCIT vs Placebo, in the change in mean TNSS after 12 months of treatment between the placebo and treatment arm.• Analysis: The comparison between arms will be conducted using an analysis of covariance (ANCOVA) model, where the change from baseline to 12-month mean TNSS score is the outcome. The ANCOVA model will include fixed categorical effects for treatment and baseline mean TNSS score, with adjustment for site. Least square means (LSmeans) and associated SEs will be presented for each treatment group. The comparison between treatment groups will be presented using the LSmeans difference and associated 2-sided 95% confidence interval (CI) and p-value.

National Institute of Allergy and Infectious Diseases
{Statistical Analysis Plan - Protocol #}

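### The SAP gives two incompatible rules for its primary analysis (complete case in 8.1.3, hypothetical strategy with multiple imputation in 8.2 and 14.1) and names no lead population

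*SAP*

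**What the plan says.** - **SAP 8.1.3:** "The primary method of handling missing efficacy data will be the use of complete case analysis for the primary analyses". The next sentence leaves participants with no 12-month NAC out of the ANCOVA.
- **SAP 8.2:** every intercurrent event is handled by a hypothetical strategy, glossed as imputation, and "Missing data of this nature, as well as missing data due to withdrawal, will be multiple imputed as described above in section 7.1.3". The primary row of the estimand table (SAP 14.1) repeats both statements.
- **Population, SAP 8.2:** "the analysis population will include subjects who are in the modified ITT and per protocol populations". SAP 14.1 says much the same. Neither set is marked as leading.
- **SAP 5:** mITT is "All participants who are randomized, received at least one dose of study treatment, and receive at least one dose during the 12-month NAC". Per protocol (PP) is randomised children who "are escalated to at least 0.4 mL of the 1:10 maintenance dose, and receive at least 3 doses of maintenance SCIT/placebo"; it does not ask for a 12-month NAC.
- **Protocol 13.4.3.2:** MCMC multiple imputation is the primary method. The text names the method, the ANCOVA run on each completed data set and the pooling step, but not the variables in the imputation model.
- **Protocol 6.7 and 11.4:** children taken off therapy are "followed when possible for the duration of the study and seen for all remaining visits except Injection Visits", and those who stop after one dose "will be asked to continue study follow-up for the remainder of the treatment period".
- **SAP 2 and 12:** the SAP prevails over the protocol where they differ. The only change from the protocol that section 12 lists is the PP definition.

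**The concern.** Two analysts could each follow this SAP faithfully and run different primary analyses, on different sets of children. They could also answer different questions. Using the observed challenge whether or not injections were stopped estimates the effect of assignment to SCIT. A hypothetical strategy estimates the effect had injections not been stopped. If the text is not reconciled before unblinding, the rule and the population for the one primary test could be chosen with the results in view.

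**Working it through.** **1. Can the text be reconciled?** The two rules concern the same endpoint and the same ANCOVA.

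| Item | SAP 8.1.3 | SAP 8.2 and 14.1 |
|---|---|---|
| No 12-month NAC | left out | multiply imputed |
| Intercurrent events | not mentioned | all hypothetical; none named |
| Imputation model | none needed | refers to 7.1.3 |

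SAP 7.1 is Protocol Deviations and has no 7.1.3. The section that matches by subject is 8.1.3, which says the opposite. The precedence clause in SAP 2 ranks SAP over protocol, not one SAP section over another. Section 12 does not record a move away from MCMC imputation. A figure that is not shown follows the intercurrent-event text in 8.2, so a list there cannot be ruled out; the repeat in 14.1 has none.

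**2. Where would the rules give different results?**

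- *mITT, no challenge:* such a child is excluded by definition, so imputing after withdrawal has almost nobody to act on.
- *mITT, stopped injections but challenged at 12 months:* Protocol 6.7 and 11.4 make this possible. Complete case uses the value. A hypothetical strategy may set it aside and impute it; the SAP neither states nor excludes this.
- *PP, no challenge:* dropped under one rule, imputed under the other.
- *COVID-19 pause:* if it counts as an intercurrent event, children in the second group of SAP 8.5 would have imputed values.

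**3. The plan's own figure.** Protocol 13.6 gives a difference of 2.94 × 0.30 = 0.882, SD 1.09, 27 per arm and two-sided 0.05. The noncentrality is 0.882 / (1.09 × √(2/27)) = 2.97 on 52 df, giving power of 83.1%. The stated 83% reproduces.

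**4. Shift in target if observed values of stoppers are set aside.** The documents give no stopping rate, so p = 10/20/30% per arm is assumed. The target with observed values is 0.882 × (1 − p × share of effect lost).

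- No effect in stoppers: 0.882 × 0.90/0.80/0.70 = 0.79/0.71/0.62, against 0.88 under the hypothetical strategy.
- Half the effect kept: 0.882 × 0.95/0.90/0.85 = 0.84/0.79/0.75.

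**5. How often p < 0.05 differs.** Simulation with 80 children, 1,000 to 2,000 trials per setting. Assumed: 6 sites, baseline slope 0.5, stopping or missingness at random in both arms, and 20 imputations from the ANCOVA model pooled by Rubin's rules. The SD of 1.09 can be read in two ways. The code in Protocol 13.6 fits an intercept-only model, which suggests an unadjusted SD. The residual SD would then be 1.09 × √(1 − 0.5²) = 0.944, taking the baseline SD as 1.09 too.

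| Case (10/20/30%) | residual SD 1.09 | residual SD about 0.94 |
|---|---|---|
| Stoppers set aside, no effect in them | 6–8 / 12–13 / 17–20% | 3–5 / 7–10 / 16–17% |
| Stoppers set aside, half effect kept | 5 / 10 / 15% | 2–3 / 4–5 / 8–9% |
| Stoppers set aside, full effect kept | 6 / 10 / 16% | 1 / 4 / 9% |
| Only missing challenges imputed | 1 / 3 / 5% | 1 / 2 / 2% |

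Ranges are across repeat runs; one run of 1,000 trials gave 22% for the last entry of the first row at 1.09. In the last row the estimate is the same under both rules (about 0.89 at SD 1.09). That row fits neither set exactly: mITT cannot hold a child with no challenge, and PP would have to contain all 80 children.

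**6. A smaller inconsistency in the same model.** SAP 8.2.2 and 14.1 list baseline mean TNSS among the categorical fixed effects; SAP 8.1.3 calls it a covariate.

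**The case against.** The best case for the plan is that complete case was clearly meant and the imputation wording is left over. Much of this stands:

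- SAP 8.1.3 follows the opening of Protocol 13.4.3.2 and puts complete case in place of MCMC, which looks deliberate.
- For the responsive dose, SAP 8.3.3 and 14.1 rule out imputing missing 12-month challenges.
- mITT requires a challenge dose and is analysed as randomised, whatever was received.
- SAP 7.1.3 is probably a slip for 8.1.3. SAP 9.1 cites section 4 for samples defined in 5, and 9.4 cites 8.2 for summaries in 9.3. The slips are not all one way: 8.1.2 cites 15.1 for a schedule in 14.3.

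So a reader who infers that the text gives no hint of the intended rule goes too far. But a lean is not a decision. The imputation rule stands in both the endpoint definition and the estimand table, and the lead population stays open on any reading.

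A reader might also infer that the two rules must disagree in mITT, and take the larger percentages above as the expected effect. The documents do not support that. SAP 8.2 speaks of imputing missing data and does not say that observed challenges are discarded or that stopping injections is an intercurrent event. If only missing values are imputed, the rules barely differ in mITT.

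**Conclusion.** The contradiction is real and is in the current SAP text for the primary endpoint. Neither the precedence clause nor section 12 resolves it. It must be fixed because it leaves the primary estimand, population and missing-data rule open, not because of a particular error rate.

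The size rests on assumption. If observed challenges of stoppers are set aside and stoppers have no effect, the target moves from about 0.79/0.71/0.62 to 0.88, and significance differs in roughly 3–8/7–13/16–20% of trials at 10/20/30% stopping. If only missing values are imputed at random, the estimate does not move and significance differs in under about 5% with 80 children.

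A reader might infer from SAP 2 that database lock is still ahead. That section says only that the SAP must be final before lock, and parts of the SAP describe conduct in the past tense, so the timing is not established.

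**What to change.** Make these changes before unblinding if that is still possible; otherwise report them as a clarification in the clinical study report.

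1. Name mITT as the single primary population, as the secondary NAC and antibody analyses already do, and make PP supportive.
2. State complete-case mITT with a treatment-policy strategy, using the observed 12-month NAC whether or not injections were stopped, in SAP 8.1.3, 8.2, 8.2.2 and 14.1. Delete the hypothetical and imputation wording and the 7.1.3 reference. If the hypothetical strategy is kept instead, list the intercurrent events (including whether the COVID-19 pause is one), say whether observed values are replaced, and give the imputation model.
3. If complete case is chosen, list the departure from the protocol's MCMC imputation in SAP 12.
4. Enter baseline mean TNSS as a continuous covariate in 8.2.2 and 14.1, to agree with 8.1.3.

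Optional: an imputation-based sensitivity analysis in all randomised and dosed children. Protocol 13.4.3.2 says MCMC imputation does not rely on missing at random, whereas the standard form does; this is minor and is superseded if complete case is chosen.

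Cost: SAP wording, with a little programming if the optional analysis is added. No new data are needed.

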8.1.4. Multiple Comparisons/Multiplicity

[ICH E3; 11.4.2.5; ICH E9; 5.6](#)

As ICAC-28 is a pilot study, adjustment for multiplicity will not be performed for the primary or secondary endpoints.

8.1.5. Definitions of Outcome Measures

Many of the study endpoints derive from the nasal allergen challenge (NAC) procedure, where increasing doses of allergen are administered in defined time intervals (every 10-20 minutes) up to a specified maximum dose (up to 9 doses in ICAC-28) or a symptom threshold. After administration of each dose, staff count the number of sneezes for 10 minutes; five or more sneezes results in the maximum sneeze score of 3. After the 10 minutes have passed, participants rate their symptoms separately for runny nose, stuffy nose, and itchy nose on a scale of 0-3. The sum of the 4 symptoms is the Total Nasal Symptom Score or TNSS, which ranges from 0-12. In the ICAC-28 study, a NAC is considered positive when the TNSS ≥ 6 or the sneeze score = 3. The dose that elicits the positive response is called the NAC responsive dose. The baseline NAC is stopped at the responsive dose. The 12-month NAC is continued to its responsive dose or the baseline responsive dose, whichever is later.

8.2. Primary Endpoint

[ICH E9: 2.2.2-2.2.7](#)

Variable (Endpoint): Change in mean TNSS after 12 months of treatment with cockroach SCIT.

Population: Of all subjects defined by the study inclusion / exclusion criteria, the analysis population will include subjects who are in the modified ITT and per protocol populations.

Intercurrent events: All intercurrent events will be handled following hypothetical strategy (imputation). Missing data of this nature, as well as missing data due to withdrawal, will be multiple imputed as described above in section 7.1.3.

[figure not shown]
Population-level summary: Difference between treatment groups, Cockroach SCIT vs Placebo, in the change in mean TNSS after 12 months of treatment between the placebo and treatment arm.

8.2.1. Computation of the Primary Endpoint

The primary endpoint of the study is the change in the mean TNSS from baseline to 12 months, calculated as the difference between the mean TNSS at baseline up to their baseline responsive dose and the mean TNSS at 12 months up to their baseline responsive dose.

Below are a couple of examples describing the above calculations. The top row displays the participant's TNSS scores and bottom row displays the participants sneeze scores. The pink line is the measurement taken at baseline while the blue line is the measurement taken at 12 months.

1. Example

In this example, the participant reacted at baseline with sneeze at dose 6.

The baseline mean TNSS is calculated up to dose 6:

$$\frac{0 + 0 + 0 + 1 + 0 + 3}{6} \approx 0.7$$

The 12-month mean TNSS is calculated the same as the baseline mean:

[figure not shown]
$$\frac{2 + 0 + 0 + 0 + 0 + 0}{6} \approx 0.3$$

Then change in the mean TNSS from baseline to 12 months will be calculated as:

Page 20 of 40

$$0.3 - 0.7 = -0.4$$

2. Example

Unlike the participant in the example above, this participant reacted at baseline with TNSS, dose 4. However, the calculation of the mean and change in mean are similar.

The baseline mean TNSS is calculated up to dose 4:

$$\frac{4 + 4 + 3 + 9}{4} \approx 5$$

The 12-month mean TNSS is calculated the same as the baseline mean:

$$\frac{2 + 2 + 3 + 4}{4} \approx 2.8$$

Then change in the mean TNSS from baseline to 12 months will be calculated as:

$$2.8 - 5 = -2.2$$

8.2.2. Primary Analysis of the Primary Endpoint

ICH E3: 11.4.1

The comparison between arms will be conducted using an analysis of covariance (ANCOVA) model, where the change from baseline to 12-month mean TNSS score is the outcome. The ANCOVA model will include fixed categorical effects for treatment and baseline mean TNSS score, with adjustment for site. Least square means (LSmeans) and associated SEs will be presented for each treatment group. The comparison between treatment groups will be presented using the LSmeans difference and associated 2-sided 95% confidence interval (CI) and p-value.

8.3. Secondary Endpoints

8.3.1. Endpoint 1

Variable: Number of immunotherapy related adverse events, overall and by participant, and number of immunotherapy related serious adverse events in the course of treatment.

Analysis: Summary tables will present the total number of events as well as the number and percentage of subjects experiencing the events. If a subject experiences the same AE on multiple occasions, the event will be counted once for each occurrence when reporting the number of AEs. When reporting the number of subjects experiencing the events, a subject will only be counted once if they experience an event within the particular system organ class or preferred term. Percentages will be based on the number of subjects in the safety population.

8.3.2. Endpoint 2a

Variable: Change in TNSS AUC from baseline to 12 months, calculated as the difference between the AUC TNSS at baseline up to their baseline responsive dose and the AUC TNSS at 12 months up to their baseline responsive dose.

Analysis: For the mITT population, like the rules referenced in section 8.2.1, the TNSS AUC will be calculated separately at baseline and 12 months for each subject using the trapezoidal rule and divided by their baseline reactive dose. Change in TNSS AUC will be compared between treatment arms using an analysis of covariance (ANCOVA) model. The model will contain the change from baseline to 12-month TNSS AUC as the outcome, and fixed effects for baseline TNSS AUC, treatment group, and site. Least square means and associated SEs will be presented for each treatment group. Difference in least square means between treatment groups will be presented along with associated 2-sided 95% confidence interval (CI) and p-value.

8.3.3. Endpoint 2b

Variable: 12-Month responsive dose. 12-Month responsive dose will be calculated as the first dose for which a reaction (TNSS ≥ 6 or sneeze score of 3, whichever occurs first) occurs in the sequence of up to 9 doses.

Analysis: For the mITT population, the 12-month responsive dose will be analyzed using a Cox Regression model. This analysis, which will estimate a hazard ratio, is based on a model for the conditional probability of a subject reacting to a given dose, given that the subject has not reacted to previously administered doses. Participants who reach the last dose without reacting will be considered right censored. The baseline responsive dose and site will be controlled and there will be no imputation for missing 12-month NAC observations.

8.3.4. Endpoint 3

Variable: Change in log-transformed German cockroach-specific IgE and IgG4 from baseline to 12 months.

Analysis: For the mITT population, 12-month log-transformed IgE and IgG4 will be modeled as ANCOVA with factors for treatment arm, site, and the respective log-transformed baseline as covariates. Geometric least square means (LSmeans) and associated SEs will be presented for each treatment group. The geometric least square mean ratio comparing treatment vs placebo group, associated 95% confidence interval (CI) and p-value will be presented.

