13.4.3 Supportive Analyses of the Primary Endpoint

13.4.3.1 Effects of Cockroach SCIT on TNSS

Additionally, it will be possible to compare the responsive dose at the 12-month NAC (the dose which elicits the threshold response of a TNSS ≥ 6 or a sneeze score ≥ 3) at the 12-month NAC by treatment group, using discrete-time (discrete-dose) survival analyses as described by Chinchilli et al.³⁰ and Sampson et al.³¹ This analysis, which will estimate a hazard ratio, is based on a model for the conditional probability of a subject reacting to a given dose, given that the subject has not reacted to previously administered doses. Details of right censoring, adjustment for the baseline NAC, imputation for missing 12-month NAC observations, and evaluation of the proportional hazards assumption (and analytical options when the assumption is not met) will be provided in the Statistical Analysis Plan.

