Efficacy Category 2	Secondary/MCP	
Variable: Change in TNSS AUC from baseline to 12 months. AUC at baseline will be calculated from the TNSS score across 9 doses or until reaction (TNSS \geq 6 or sneeze score of 3, whichever occurs first). The TNSS AUC at 12-months will be calculated from the TNSS score across 9 doses or until TNSS = 12 or the baseline reacting dose has been reached, whichever occurs first.For the mITT population, like the rules referenced in section 8.2.1, the TNSS AUC will be calculated separately at baseline and 12 months for each subject using the trapezoidal rule and divided by their baseline reactive dose. Change in TNSS AUC will be compared between treatment arms using an analysis of covariance (ANCOVA) model. The model will contain the change from baseline to 12-month TNSS AUC as the outcome, and fixed effects for baseline TNSS AUC, treatment group, and site. Least square means and associated SEs will be presented for each treatment group. Difference in least square means between treatment groups will be presented along with associated 2-sided 95% confidence interval (CI) and p-value.
	Secondary/MCP	
Variable: Change in Responsive dose from baseline. Responsive dose will be calculated as the first dose for which a reaction (TNSS \geq 6 or sneeze score of 3, whichever occurs first) occurs in the sequence of up to 9 doses.Analysis: For the mITT population, compare the change in responsive dose (the dose which elicits the threshold response of a TNSS \geq 6 or a sneeze score \geq 3) from baseline to the 12-month NAC between treatment groups, using discrete-time (discrete-dose) survival analyses^{1,2}. This analysis, which will estimate a hazard ratio, is based on a model for the conditional probability of a subject reacting to a given dose, given that the subject has not

¹

²

National Institute of Allergy and Infectious Diseases
 {Statistical Analysis Plan - Protocol #}

[figure not shown]
		reacted to previously administered doses. Participants who reach the last dose without reacting will be considered right censored. The baseline NAC responsive dose and site will be controlled and there are no imputations for missing 12-month NAC observations.

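### SAP 8.3.3 and SAP 14.1 name different survival models and different variables for the responsive-dose endpoint, and with at most nine doses the unstated tie method affects the hazard ratio and p-value

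*SAP*

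**What the plan says.** Responsive dose is item 2b of the secondary endpoints (Protocol 3.3, SAP Section 3). It is described in three places.

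- **SAP 8.3.3** states that "the 12-month responsive dose will be analyzed using a Cox Regression model". The variable is the 12-month value: "12-Month responsive dose will be calculated as the first dose for which a reaction" (TNSS of at least 6, or sneeze score 3) "occurs in the sequence of up to 9 doses". The next sentence says that the analysis "is based on a model for the conditional probability of a subject reacting to a given dose", given no reaction at earlier doses. Censoring is stated: "Participants who reach the last dose without reacting will be considered right censored". Baseline responsive dose and site are covariates. No tie method is given.
- **SAP 14.1** names the variable "Change in Responsive dose from baseline" and compares it between arms "using discrete-time (discrete-dose) survival analyses". The censoring rule and covariates match 8.3.3. No link function is given.
- **Protocol 13.4.3.1** compares the 12-month responsive dose "using discrete-time (discrete-dose) survival analyses as described by" two cited papers. It leaves the evaluation of proportional hazards, and the options if that assumption fails, to the SAP.

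SAP Section 2 gives the SAP precedence over the protocol but does not rank the SAP's body against its appendix. SAP Section 12 lists one change from the protocol, the per-protocol definition.

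**The concern.** A programmer working from 8.3.3 fits a Cox model; one working from 14.1 fits a discrete-time model. Both follow the SAP. The sentence kept under the Cox label in 8.3.3 describes the discrete-time model, so the text does not show whether the switch was intended.

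The choice matters because the axis is coarse. The partial likelihood assumes a continuous event time, and any tie method is an approximation or an alternative to it. Here the event time is a dose number from 1 to 9 and nearly every event is tied. The tie method then affects both the estimate and the test. On the discrete-time side, the unstated link decides whether a hazard ratio or an odds ratio is reported.

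The variable label adds a second conflict. A change in responsive dose can be zero or negative, so it cannot be the sequence of administered doses over which a conditional probability of reacting is modelled. What is at stake is the hazard ratio, its interval and its p-value for one of the two secondary nasal-challenge endpoints.

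**Working it through.** **1. The plan's own figures.** The documents give no power, hazard ratio or event count for responsive dose. The only power statement, in Protocol 13.6, is for mean TNSS: 83% with 54 participants, difference 0.88, SD 1.09, two-sided 0.05. A noncentral t calculation with 27 per arm gives 82.9%. That figure stands and is not touched by this point. Its 54, and the planned enrolment of 80, serve below as sample sizes.

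**2. What each method estimates at one dose.** Let the placebo conditional probability of reacting at a dose be h, and the hazard ratio 0.5 (assumed). Under grouped proportional hazards the active-arm probability is 1 − (1 − h)^0.5.

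With d1 of n1 active and d0 of n0 placebo participants reacting at a single dose, the Breslow score equation is d1 = (d0 + d1)·n1θ/(n0 + n1θ). It solves to θ = (d1/n1)/(d0/n0), the ratio of conditional probabilities. A logit link gives the odds ratio. A complementary log-log link gives the hazard ratio.

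| h (assumed) | active probability | Breslow target (ratio) | logit target (odds ratio) | cloglog target |
|---|---|---|---|---|
| 0.10 | 1 − 0.9487 = 0.0513 | 0.513 | 0.0541/0.1111 = 0.487 | 0.50 |
| 0.25 | 1 − 0.8660 = 0.1340 | 0.536 | 0.1547/0.3333 = 0.464 | 0.50 |
| 0.50 | 1 − 0.7071 = 0.2929 | 0.586 | 0.4142/1 = 0.414 | 0.50 |

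The more reactions gather on one dose, the further Breslow moves toward 1 and the logit away from it.

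**3. Whole-challenge simulation, no site terms.** Nine doses, 1:1 allocation, true hazard ratio 0.5, one fitted standard-normal prognostic covariate, Wald test at 1.96, 1,500 runs per cell (Monte Carlo SE about 1.3 points). Three assumed placebo patterns: late (34% never react), spread (13%) and clustered (2%). Entries are geometric-mean hazard ratio / power.

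| N | pattern | events | ties at busiest dose | Breslow | Efron | cloglog |
|---|---|---|---|---|---|---|
| 54 | late | 29.0 | 7.3 | 0.506 / 38.1% | 0.485 / 42.4% | 0.478 / 43.9% |
| 54 | spread | 40.6 | 8.8 | 0.527 / 48.8% | 0.494 / 56.9% | 0.484 / 59.1% |
| 54 | clustered | 48.6 | 14.9 | 0.559 / 48.7% | 0.498 / 64.0% | 0.477 / 67.7% |
| 80 | late | 43.1 | 10.1 | 0.520 / 54.1% | 0.499 / 58.9% | 0.494 / 59.7% |
| 80 | spread | 60.2 | 12.1 | 0.534 / 67.5% | 0.501 / 74.1% | 0.494 / 75.5% |
| 80 | clustered | 72.1 | 21.5 | 0.559 / 68.8% | 0.498 / 82.1% | 0.482 / 83.3% |

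Breslow power is below cloglog by 43.9 − 38.1 = 5.8, then 10.3, 19.0, 5.6, 8.0 and 14.5 points. Efron is below cloglog by 0.8 to 3.7 points. A logit link gave odds ratios of 0.41 to 0.47.

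**4. Null rejection, same set-up** (true hazard ratio 1, spread and clustered only, 500 runs, SE about 1 point): Breslow 1.0% to 3.4%, Efron 3.2% to 6.4%, cloglog 5.2% to 8.0%. Part of the power gap in step 3 is therefore a difference in actual test size.

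**5. With baseline and site terms fitted.** The documents do not give the number of sites, so it is assumed. Two further simulations used eight allergen doses.

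- 8 sites, 800 runs per cell, N = 54: null rejection was cloglog 10–12%, Efron 8–9%, Breslow 3–5%. Estimates of a true 0.5 were 0.43–0.46, 0.45–0.47 and 0.49–0.52. At N = 80 null rejection was 7.5–8.7%, 6–7% and 2–4%.
- 4 to 8 sites, 300 runs per cell, N = 54: null rejection was cloglog 7–8%, Efron 6–8%. Estimates were 0.45–0.47 and 0.47–0.49.

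Many site parameters in a small sample push all estimates away from 1. Breslow's attenuation offsets that, which is why it then lands near 0.5.

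**The case against.** The strongest reply is that little is wrong beyond wording. The SAP outranks the protocol, so that half of the conflict is settled. Both SAP sections define the responsive dose as the first reacting dose, censor alike and adjust for the baseline dose, so the word change is probably a label carried over from the endpoint list. The study is described as a pilot without multiplicity adjustment (SAP 8.1.4), and Protocol 13.4.3 places this comparison among supportive analyses.

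Most of that is fair, and it limits the weight of the point. It does not resolve 8.3.3 against 14.1, supply a tie method, or explain why Section 12 is silent.

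Three stronger readings are tempting and do not hold:

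- **That Cox regression is the wrong model here.** Cox with Efron ties recovers a true 0.5 as 0.49 to 0.50 in step 3, at almost the power of the discrete-time model. The harm comes from unspecified tie handling.
- **That the trial will lose 6 to 19 points of power.** The SAP does not call for Breslow ties and names no survival software. The reaction patterns and hazard ratio are assumptions, and the comparison narrows once test size and site terms are considered.
- **That a complementary log-log model with site terms is simply better.** With site terms it over-rejected at least as much as Efron in the simulations and overstated the effect more.

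**Conclusion.** The contradiction is real. It lies within the SAP as well as between SAP 8.3.3 and the protocol, and it is not declared. One secondary endpoint has two models, two variable labels, no tie rule and no link, so its hazard ratio and p-value are not fixed in advance.

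The size depends on what is programmed. Without site terms, Breslow ties move the hazard ratio toward 1 by about 5% to 17% relative to the complementary log-log fit (0.520/0.494 = 1.05; 0.559/0.477 = 1.17) and make the test conservative. Efron ties differ little from that fit. With site terms, Breslow remains the most conservative of the three, but its estimate can fall close to the true value because two biases offset. All these figures rest on assumed hazard ratios, reaction patterns and site numbers.

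The point should be corrected before database lock. It does not threaten the primary analysis or the sample size.

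**What to change.** 1. Name the same single model in SAP 8.3.3 and 14.1. Either choice is acceptable:
   - Cox regression with Efron ties, or exact ties in the continuous-time sense. The discrete form of the exact likelihood is a conditional logistic model and yields an odds ratio.
   - A discrete-time binomial model with dose-level intercepts and the link stated: complementary log-log if a hazard ratio is to be reported.
2. If the discrete-time model with site terms is chosen, acknowledge its small-sample over-rejection. Limit the site parameters, for example by pooling small sites, or specify a small-sample-robust test such as re-randomisation within site. The same caution applies, to a lesser degree, to Cox with Efron ties and site terms.
3. Define the variable in both sections as the 12-month responsive dose, with baseline responsive dose as a covariate. Add a line saying that this is how the change worded in the endpoint list (Protocol 3.3, SAP Section 3) is analysed.
4. Record the choice in SAP Section 12.
5. Add the proportional-hazards evaluation that Protocol 13.4.3.1 left to the SAP, for example a treatment-by-dose term, and state what will be reported if the assumption fails.

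The cost is a few sentences of SAP text and standard model code, with no new data and no change to trial conduct.
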